10.2.23 Blood Volume Collection Summary

An estimated 20 to 55 mL of blood is required to be drawn at clinic visits, with an estimated total of 350 mL expected during this study (refer to details in the Laboratory Manual).

11 ADVERSE EVENT REPORTING

At each study visit, patients will be evaluated for new AEs and the status of existing AEs. All AEs from the time the informed consent is signed through the EOS Visit 27/Week 29 will be recorded on the eCRF.

11.1 Definition of Adverse Events

11.1.1 Adverse Event (AE)

An AE is any untoward medical occurrence in a clinical study patient, whether or not the event is considered causally related to the investigational product. An AE can be a new occurrence or an existing process that increases significantly in severity or frequency.

Adverse events include:

- Symptoms described by the patient or signs observed by the Investigator or medical staff
- Test abnormalities (laboratory tests, ECG, x-rays, etc.) that result in an alteration in medical care (diagnostic or therapeutic)
 - Abnormally low values for C3, C4 or A:G ratio may result in discontinuation of study treatment. Patients who discontinue due to these laboratory test abnormalities will be classified as “withdrawals due to adverse events” and a narrative describing their history and reason for withdrawal will be prepared by the Investigator.
 - Abnormally low eGFR or platelet count or abnormally high urine protein as described in Table 3 may result in discontinuation of study treatment. Patients who discontinue due to these laboratory test abnormalities will be classified as “withdrawals due to adverse events”.
- Injury or accidents. Note that if a medical condition is known to have caused the injury or accident (a fall secondary to dizziness), the medical condition (dizziness) and the accident (fall) should be reported as 2 separate AEs. The outcome of the accident (hip fracture secondary to the fall) should be recorded in source documents.

Abnormalities present at Baseline are considered AEs only if they reoccur after resolution or worsen in severity or frequency during the study.

Each AE is to be classified as serious or nonserious.

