Treatment for DM usually involves a combination of approaches with a focus on controlling the skin and muscle disease. Currently, there are only 2 drugs approved for the treatment of DM, Acthar gel (a highly purified sterile preparation of adrenocorticotrophic hormone [ACTH]) and

prednisone; all other pharmacologic interventions are used off-label. Skin disease may be treated by avoiding sun exposure (as the cutaneous manifestations are extremely photosensitive) and/or with topical corticosteroids, antimalarial agents, immunomodulatory medications and intravenous immunoglobulin (IVIG) (Ang 2005, Levine 2012). Muscle weakness is also most commonly treated with corticosteroids, typically in conjunction with an immunosuppressive agent. Patients may also require assistive devices for ambulation, as well as adaptive strategies to minimize gastrointestinal complications secondary to esophageal muscle weakness, e.g., elevation of head of bed, avoidance of eating before bedtime.

Unfortunately, many patients do not achieve full control of symptoms with prednisone and/or experience intolerable side effects, including infection, weight gain, mood/behavioral changes, osteoporosis, Cushing's disease, and diabetes (Harris 2015). Glucocorticoids have also been associated with myopathy, which is a serious concern for patients with DM (Schakman 2009). Thus, there is an unmet medical need for safe and effective treatments for patients with DM.

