11.2 Evaluation of Adverse Events

All AEs/SAEs experienced by the patient will be recorded in the eCRF and will include a concise description of: the event; date and time of event onset and resolution; relationship to study drug; severity; management of study medication; management of the AE/SAE, and outcome as described in Sections 11.2.1 through 11.2.7.

Abnormalities in vital signs, laboratory results, and other safety assessments will be recorded as an AE if they meet the definition of an AE (Section 11.1).

When possible, a diagnosis should be recorded as an AE, rather than symptoms or isolated laboratory abnormalities related to that diagnosis.

A medical or surgical procedure is not an AE; rather the condition leading to the procedure should be recorded as the AE. If the condition is not known, the procedure must be reported as an AE instead.

Similarly, death is not an AE, but is rather the outcome of the AE(s) that resulted in death. If the AE(s) leading to death are not known, then death must be reported as an AE.

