14.4.5.3 Adverse Events

Adverse events will be coded using the Medical Dictionary for Regulatory Activities (MedDRA) and tabulated by event, severity, and relationship to study therapy. Listings of SAEs and AEs

leading to study discontinuation will be produced. A listing of verbatim AE terms and the MedDRA terms they are mapped to will be produced.

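### The note on accidents in Section 11.1.1 sends the resulting injury to source documents without calling for an AE record, which contradicts the protocol's own AE rules

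*Protocol*

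**What the plan says.** Section 11.1.1 opens with a broad definition: "An AE is any untoward medical occurrence in a clinical study patient", whether or not it is thought to be caused by the product. Its list of what counts as an AE includes "Injury or accidents". A note under that item covers the case where a medical condition is known to have caused the event: "the medical condition (dizziness) and the accident (fall) should be reported as 2 separate AEs". The next sentence deals with the consequence: "The outcome of the accident (hip fracture secondary to the fall) should be recorded in source documents".

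Section 11 puts every AE from consent to the end-of-study visit on the eCRF. AEs are a primary safety endpoint in Section 6.1.1.1 and in the synopsis. Under Section 14.4.5.3 they are coded in MedDRA and "tabulated by event, severity, and relationship to study therapy".

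**The concern.** The note sets the number of AEs at two and names another destination for the third event. Source documents are neither coded nor tabulated. If a site takes the example at face value, the injury has no AE row, severity grade or causality assessment. The statistical analysis plan could not repair this later, because it cannot tabulate what the eCRF did not collect.

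The setting makes the example more than academic. Section 4.2 describes proximal weakness that includes the hip flexors, and it lists prednisone side effects "including infection, weight gain, mood/behavioral changes, osteoporosis" among others. Section 7.1 permits stable background prednisone. The study is planned for approximately 20 centers and 36 patients, so sites could plausibly resolve the contradiction in different ways.

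**Working it through.** No arithmetic applies, because the point depends on no rate, power or sample-size figure. The check sets the rules side by side and follows the protocol's own example through them.

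**The example under the note**

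| Event | Instruction in the note (11.1.1) | Coded AE row |
|---|---|---|
| Dizziness | AE | yes |
| Fall | AE | yes |
| Hip fracture | source documents | none called for |

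**The same fracture under the other rules**

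- Section 11.1.1, definition: a fracture is an untoward medical occurrence, so it is an AE.
- Section 11.1.1, list: injuries are named as AEs. X-ray abnormalities that change medical care are named too.
- Section 11: all AEs go on the eCRF.
- Section 10.2.22: the indication for any new medication or therapy is recorded as an AE. A treated fracture is such an indication.
- Section 11.2: where a procedure is performed, the AE is the condition that led to it. For a surgical repair, that condition is the fracture.

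The note therefore points one way and these rules point the other.

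**Does the note mean source documents alone?** It does not say so. However, where the protocol wants both records it names both: Section 8.4.2 (details of unblinding), Section 9 (medications), and Sections 9.2 and 9.3.1 (washout dates). The note names source documents and leaves out the eCRF. The AE outcome field in Section 11.2.7 does not fill the gap, since its categories describe how an event ended and do not identify a new injury. Reading the note as excluding an AE record is an inference, but a reasonable one for a site to make.

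**What reaches the data if the note is followed literally**

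1. The fall leads to admission for the fracture. Under Section 11.1.2 the fall is an SAE, since hospitalization as a consequence of the event counts. Section 11.3 then brings in detailed descriptions and hospital reports. The case reaches the safety data, but the coded term may be only the fall.
2. The injury is managed without admission and meets no other seriousness criterion. No SAE report is triggered by it. Unless the site applies Section 10.2.22 or 11.2 in preference to the note, the injury stays in source documents.

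**The case against.** The best defence is that the note is one loosely worded illustration surrounded by rules that would usually capture the fracture. An injury serious enough to matter would normally be treated, and then Section 10.2.22 or Section 11.2 makes it an AE. A hospitalized case is reported as an SAE through the fall. Section 11.2.1 asks for descriptions as specific and complete as possible, and Section 14.4.5.3 lists verbatim terms. Safety analyses are descriptive (Section 14.4.5), so no formal comparison would be lost.

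Much of this stands, and it limits the finding. It does not remove it: those rules are exactly what the note contradicts, and a worked example is likely to guide site staff more than a general definition.

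Some stronger readings are tempting but not supported:

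- A reader might infer that fractures and other injuries never reach the AE data, or that every accident-related injury is lost. The rules above would often capture them, and the note concerns only the consequence of an accident, illustrated by one with a known medical cause.
- A reader might cite the rule "When possible, a diagnosis should be recorded as an AE, rather than symptoms or isolated laboratory abnormalities related to that diagnosis" as a further contradiction. Dizziness and a fall are not symptoms of a hip fracture, so that rule does not apply.
- A reader might say that seriousness is attached to the wrong term. Section 11.1.2 properly makes the fall serious if admission follows from it. What may be missing is a separate record for the injury.
- A reader might treat one missed event in an arm of 12 (1/12 = 8.3%) as the size of the problem. That is only one patient's share of an arm. The protocol gives no fracture rate. Muscle weakness is not required for entry (Section 7.1), and prednisone is permitted but not required.

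**Conclusion.** Wrong as written. The note in Section 11.1.1 states a recording rule that contradicts the AE definition and injury item in the same section, as well as Sections 10.2.22, 11 and 11.2. Followed literally, it can leave injuries resulting from accidents out of the coded AE tables, especially those that do not meet SAE criteria. Serious ones may be coded only as a fall.

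In the protocol's example, one of three events lacks its own AE record. How many events would be affected cannot be estimated from the document. The conclusion assumes that some sites would read the note as replacing, not adding to, an AE entry for the injury. The wording allows that reading but does not compel it. Injuries outside the note's scope remain AEs.

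**What to change.** Reconcile the passages by replacing the last sentence of the note with: *The injury resulting from the accident (e.g., hip fracture) is also recorded as an AE on the eCRF with its own severity, causality and seriousness.* Align the eCRF completion guideline so that sites see the same instruction at data entry.

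The cost is one protocol sentence, one guideline line, and at most an additional AE record per resulting injury. Treatment, visits, sample size and the planned analyses do not change.

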11.1.2 Serious Adverse Events (SAE)

An AE is serious when the patient outcome, regardless of whether or not it is considered related to the study medication, is one or more of the following:

- Death
- Life threatening, per the Investigator, the patient was at immediate risk of death from the event at the time that the event occurred. It does not include an event that hypothetically might have caused death if it had occurred in a more severe form

- Hospitalization, initial or prolonged, meaning that a hospital admission and/or prolongation of a hospital stay was required for the treatment of the AE, or occurred as a consequence of the event. It does not include a pre-planned elective hospital admission for treatment or diagnostic procedures
- Disability or incapacity that is persistent or significant
- Congenital anomaly or birth defect that occurs in the offspring of a patient exposed to the study drug
- Important medical event that, although not immediately life-threatening, requires intervention in order to prevent one of the other serious outcomes listed above

11.1.3 Suspected and Unexpected Serious Adverse Reaction (SUSAR)

A SUSAR is defined as an SAE that meets **both** the following criteria with respect to study drug:

- *Suspected* — is assessed as related or possibly related to study drug (see Section 11.2.3)
- *Unexpected* — compared to the study drug-related AEs described in Investigator's Brochure, the event meets *any* of the following criteria:
 - The event was not previously described;
 - The event is now characterized as more severe (see Section 11.2.4)
 - The event is now characterized more specifically (e.g., an event of “interstitial nephritis” in a patient receiving an agent previously described as associated with “acute renal failure”).

11.2 Evaluation of Adverse Events

All AEs/SAEs experienced by the patient will be recorded in the eCRF and will include a concise description of: the event; date and time of event onset and resolution; relationship to study drug; severity; management of study medication; management of the AE/SAE, and outcome as described in Sections 11.2.1 through 11.2.7.

Abnormalities in vital signs, laboratory results, and other safety assessments will be recorded as an AE if they meet the definition of an AE (Section 11.1).

When possible, a diagnosis should be recorded as an AE, rather than symptoms or isolated laboratory abnormalities related to that diagnosis.

A medical or surgical procedure is not an AE; rather the condition leading to the procedure should be recorded as the AE. If the condition is not known, the procedure must be reported as an AE instead.

Similarly, death is not an AE, but is rather the outcome of the AE(s) that resulted in death. If the AE(s) leading to death are not known, then death must be reported as an AE.

11.2.1 Description of Event

The diagnosis or description will be as specific and complete as possible (i.e., “lower extremity edema”, rather than just “edema”). Whenever possible, signs and symptoms due to a common etiology will be reported as an integrated diagnosis; for example, cough, runny nose, sneezing, sore throat and head congestion would be reported as “upper respiratory infection”.

11.2.2 Date and Time of Onset

The date and time at which the event was first apparent. The time of onset of symptoms may be appreciably earlier than the date and time the Investigator becomes aware of the event. Some events may be apparent to the patient and Investigator independently, and information from each may contribute to the final report. For example, a patient may report the onset of a rash two days before being seen by a physician who makes a diagnosis of herpes zoster based on appearance and laboratory confirmation. In that case, there is a single AE, with the date of onset based on the date of the initial observation by the patient and a specific description (herpes zoster) based on the clinical exam and tests.

11.2.3 Relationship to Study Drug

A causality assessment must be provided for all AEs. This assessment must be made by the Investigator and recorded on the eCRF (SAE form, as appropriate). The definitions for the causality assessment are provided below.

- **Not related:** The AE is clearly not related to study drug
- **Possibly related:** There is some evidence supporting the possibility of a causal relationship between study drug and the AE, i.e., the event follows a reasonable temporal sequence from the time of study drug administration and/or follows a known response pattern to the study drug, but could also have been attributed to other factors. AEs that are deemed by the Investigator to be possibly related to study drug shall be considered related to study drug.
- **Probably Related:** There is strong evidence that there is a causal relationship between study drug and the AE

As previously noted in Section 8.3.5, any SAE assessed by the Investigator as possibly related or probably related to study drug will require discontinuation of study drug administration according to the procedures outlined in Section 11.5; the Investigator will assess if study drug administration will be discontinued in any patient who experiences an SAE that is assessed as not related to study drug.

11.2.4 Severity

The severity of all AEs will be assessed by the Investigator as mild, moderate, or severe using the following criteria:

- **Mild:** An AE that is transient, requires minimal or no treatment, and does not interfere with the patient’s daily activities

- **Moderate:** An AE that is usually alleviated with specific therapeutic intervention. The event interferes with usual activities of daily living, causing discomfort, but poses no significant or permanent risk of harm to the research participant
- **Severe:** An AE that interrupts usual activities of daily living, or significantly affects clinical status, or may require intensive therapeutic intervention

Changes in the severity of an AE must be recorded in the eCRF to allow an assessment of the duration of the event at each level of severity. Adverse events characterized as intermittent require documentation of onset and duration of each episode if the severity of the intermittent event changes.

11.2.5 Action Taken with Study Medication upon Occurrence of an Adverse Event

For each AE the Investigator will be required to document the action taken regarding study drug in response to the AE. Options include:

- **Discontinued (withdrawn):** Study drug was stopped permanently due to the AE
- **Dosing Interrupted:** Study drug regimen was modified by being temporarily halted, i.e., one or more doses were not administered, but drug was not stopped permanently
- **Dose Not Changed (none):** No change in the administration of study mediation

11.2.6 Actions Taken for Management of AE

AEs will be followed and managed by the Investigator, including obtaining any supplemental studies needed to define the nature and/or cause of the event (e.g., laboratory tests, diagnostic procedures, consultation with other health care professionals).

For each AE the Investigator will categorize the actions taken to manage the AE as follows:

- **Concomitant medication:** One or more medications (prescription or over-the-counter) were started or increased in dose; non-medication actions may also have been ordered
- **Other action:** Non-medication action(s) were ordered as management of the AE (e.g., bed placed in Trendelenburg position, warm compresses applied to IV access site)
- **No action:** No actions were ordered for management of the AE

11.2.7 Outcome of AEs

If possible, AEs will be followed until resolved (synonyms: recovered, recuperated, ended) either with or without sequelae, or the Investigator assesses them as chronic or stable.

The outcome of each event (including date and time) will be described using the following categories:

- **Recovered:** The event resolved and patient returned to baseline
- **Recovered With Sequelae:** The event resolved but the patient is left with residual problems (e.g., functional deficits, pain)

- **Not Recovered:** At the last observation, the event was unchanged
- **Death (Fatal):** To be used for the one AE which, in the judgment of the Investigator, was the primary cause of death
- **Unknown:** There were no observations after the onset (initial observation or report) of the event

A patient withdrawn from the study because of an AE must be followed by the Investigator until clinical recovery is complete and laboratory results have returned to normal, or until progression has been stabilized. Follow-up may need to continue after the patient has discontinued from the study, and additional investigations may be requested by the Investigator. (see Section 11.4 for additional details on AE/SAE follow-up requirements).

11.2.8 Injection Site Reactions

New ISRs will be captured in AE reporting, and assessment of all previously used injection site(s) will be made at all clinic and non-clinic visits before and after dosing, and at the EOT and EOS Visits. In addition, on dosing days, the planned injection site will be assessed to confirm it is appropriate for use. ISRs that are reported by the patient or observed by the Investigator will be recorded by verbatim term, onset date, resolution date, anatomical location, and the visit number or date of the injection associated with the reaction. The verbatim terms of pain, tenderness, pruritis, induration, erythema, blisters, ulceration, and necrosis will be offered in the eCRF to simplify data collection and reporting, and Investigators will rate the severity as mild, moderate, or severe. An ISR may be composed of more than one AE using more than one verbatim term.

For ISRs of induration, erythema, blisters, ulceration, and necrosis, Investigators will measure and record the largest edge-to-edge lesion distance in millimeters.

11.3 Reporting Serious Adverse Events

The Investigator will review each SAE and evaluate the severity and the causal relationship of the event to study drug. All SAEs will be recorded from signing of informed consent until the EOS Visit 27/Week 29. Serious AEs occurring after the EOS Visit and coming to the attention of the Investigator must be reported only if there is (in the opinion of the Investigator) reasonable causal relationship with the study drug.

The Investigator is responsible for providing notification to the CRO of any SAE, whether deemed study drug-related or not, that a patient experiences during their participation in study within 24 hours of when he or she became aware of the event.

As a minimum requirement, the initial notification should provide the following information:

- Study number
- Patient number
- Name of Investigator
- Adverse event
- Criterion for classification as ‘serious’

- Study drug name
- Causality assessment (if sufficient information is available to make this classification)
- Identifiable reporter of event

CRO Safety personnel will request clarification of omitted or discrepant information from the initial notification. The Investigator or an authorized delegate is responsible for sending the requested information within 24 hours.

Initial reports of SAEs must be followed later with detailed descriptions, including clear photocopies of other documents as necessary (e.g., hospital reports, consultant reports, autopsy reports), with the study patient's personal identifiers removed. If a new SAE Report Form is sent, then the Investigator must sign and date the form. The CRO may also request additional information on the SAE, which the Investigator or an authorized delegate must send to the SAE contact information below.

SERIOUS ADVERSE EVENT REPORTING INSTRUCTIONS

PAREXEL Clinical Studies Safety Center

United States (US) Telephone number/SAE Hotline: Durham, NC [contact]

[contact]

US Email: [contact]

United Kingdom (UK) Telephone number/SAE Hotline: Uxbridge [name]

Fax number: Uxbridge [name]

UK Email: [contact]

Provide the name of the Investigator, your name, the telephone number where you can be reached, and the protocol number and title.

